Appendix 2.7. Ambulatory Glucose Profile

The following standardized glucose summary reports from ambulatory glucose profile (AGP) will be generated, at treatment-group level and individual patient level by visit, based upon the observed CGM measures:

- 24-hour period
- 0 to 4 hours relative to meal starting time for morning meal, midday meal, evening meal and across all meals.

Appendix 2.8. Derivation for CGM Variables

By-meal CGM outcome variables will be derived for each meal and across all meals based on the valid CGM sessions (Appendix 2.2).

If any concentration below lower limit of quantification (LOQ) or above upper LOQ are identified, they will be treated as LOQ for calculation of the CGM parameters. No missing CGM values will be imputed.

Since the CGM values may not be measured at the exact same time for each day for a specific individual patient, due to device changes or gaps in usage, non-overlapping intervals ('buckets') of 5 minutes over 00:00:00 to 23:59:59 (00:00:00 to 00:04:59, 00:05:00 to 00:09:59, etc.) will be used for any derivations requiring time-matched measurements across days within a visit (eg, mean of daily difference [MODD]).

All CGM glucose derivations will be conducted in units of mg/dL and mmol/L will also be provided by the conversion factor of 0.0555 from mg/dL.

Appendix 2.8.1. Incremental Area under The Glucose Curve (iAUC)

For a valid CGM meal session (with at least 70% of measures during the 0 to T hour[s] after the start of a specific meal) on a valid CGM day, $iAUC_{0-T}$ will be calculated as the sum of areas of all individual trapezoids within the time frame:

$$iAUC_{0-T} = \sum_{i=1}^k \frac{(G_i - G_0) + (G_{i-1} - G_0)}{2} \Delta t_i$$

where G_i is glucose value at a particular time, G_0 is the glucose level before the start of the given meal (using the average values within the time window [-19, 0] minutes relative to the start of the meal), Δt_i is the time interval between consecutive glucose measures, k is the total number of trapezoids within the time frame 0- T and G_k is the glucose level at the end of the time frame 0- T (using the average values within the time window [0, 14] minutes relative to the last time point of the time frame). The derivation requires that G_0 and G_k values are both available and the next meal starts after the end of the time frame 0- T .

$iAUC_{0-T}$ will be calculated for valid meal sessions and the average of a visit will be used in the analysis.

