Appendix 2.2. General Considerations

The Dexcom G6® Continuous Glucose Monitoring System (Dexcom G6) will be used in CGM addendum I8B-MC-ITSB(3.1). Patients who choose to participate in the Study ITSB CGM addendum (3.1) will use the Dexcom G6 system during 2 periods of time, prior to baseline and prior to the 26-week primary endpoint. The Dexcom G6 will be worn for up to 10 consecutive days per period.

The CGM Population includes all randomized patients who have an informed consent for the CGM addendum signed by parent(s)/legal guardian(s) and valid CGM data at baseline (Visit 4) or primary endpoint (Visit 15). Unless otherwise specified, the analyses of the CGM addendum will use the CGM Population. The data collected after permanent discontinuation of investigational product or during days when patients are temporarily off study treatment will be excluded. There will be no multiplicity adjustment.

To ensure that the CGM outcome variables are only calculated from valid CGM days with sufficient data within the 24-hour, the following criterion will be used to determine a valid CGM day: minimum number of measures per day – at least 70% of the total measures (288 measures per day) that are supposed to be obtained. All the CGM derivations are based on the data from the valid CGM days with sufficient data defined above unless otherwise specified.

Patients will be instructed to capture the start time of 3 main meals (morning meal, mid-day meal, evening) when accompanied by prandial insulin dose during each CGM session in the patient CGM diary page. The start time will be used to derive the CGM meal related outcomes for each meal and across all meals. On valid CGM days, the meal related outcomes will also use the 70% cut-point to determine a valid CGM session for the variable derivation. For example, the $iAUC_{0-2hr}$ after the morning meal for a day requires at least 70% of the 24 measures (ie, at least 17 measures) during the 2 hour time window after the start of the morning meal. If the analysis time window covers the start time of the next meal (assuming $TN0$ relative to the start time of the given meal and $TN0 < T$) and the number of non-missing measures within 0 to $TN0$ is greater than 70% of measures within 0 to T , the derivation of the meal related outcomes within 0 to T

will be based on the data from time 0 to *TNO*. Only the first meal of each type per day will be included in derivations

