Appendix 2.4. Primary CGM Outcome and Methodology

The primary outcome of the CGM addendum is the iAUC0-2hr after meals obtained from up to 10 days of CGM use at Week 26. The derivation of the iAUC0-2hr for each visit is outlined in [Appendix 2.8](#).

An ANCOVA model with treatment, type of basal insulin, hemoglobin A1c (HbA1c) stratum [$\leq 8.0\%$ or $> 8.0\%$], and age group as fixed effects and baseline as a covariate will be used for treatment group comparison. At Week 26, the treatment difference and LS mean of the difference estimated from the model will be provided.

If the percentage of the patients with missing baseline values is higher than 20% of the CGM Population, a constrained longitudinal data analysis model (Liu et al. 2009; Lu 2010) will be used instead. An unstructured covariance structure will be used to model the within-patient

errors. If this analysis fails to converge, the following covariance structures will be tested in order:

- compound symmetry with heterogeneous variances
- compound symmetry without heterogeneous variances.
- First order autoregressive

The first covariance structure that converges will be used. The Kenward–Roger approximation will be used to estimate denominator degrees of freedom.

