Appendix 2.8.3. Area under The Curve

Area under the curve (AUC) will be calculated using the standard trapezoidal rule by summing the trapezoid areas between two consecutive glucose measures in the prespecified time period (eg, 24-hour, or 1 hour after the morning meal).

Similar to $iAUC_{0-T}$, corresponding AUC_{0-T} will be derived. When the analysis time window covers the start time of the next meal and the number of non-missing measures satisfies the required minimum number, standardized AUC_{0-T} will be derived.

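### SAP Appendix 2.2 and Appendix 2.8.1 give incompatible next-meal rules for iAUC, including the CGM addendum's primary endpoint, iAUC 0-2 h

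*SAP*

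**What the plan says.** The endpoint is defined in SAP Appendix 2.4: "The primary outcome of the CGM addendum is the iAUC0-2hr after meals obtained from up to 10 days of CGM use at Week 26". Appendix 2.1 also uses iAUC 0-2 h to compare LY900014+20 with Humalog, and Appendix 2.9 lists iAUC over 0-1, 0-3 and 0-4 h among the derived variables.

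The next-meal situation is handled in four places:

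- **Appendix 2.2 (General Considerations).** The rule is triggered thus: "If the analysis time window covers the start time of the next meal". With the next meal at TN0, before the window end T, the session is retained if the non-missing readings before TN0 exceed 70% of those in the full window. Every meal-related outcome of that session then "will be based on the data from time 0 to" TN0.
- **Appendix 2.8.1 (iAUC).** The derivation requires that the start and end values G_0 and G_k "values are both available and the next meal starts after the end of the time frame". The quantity itself "will be calculated as the sum of areas of all individual trapezoids within the time frame", with no divisor.
- **Appendix 2.8.2 (average excursions).** Only excursions before the next meal are averaged.
- **Appendix 2.8.3 (AUC).** "When the analysis time window covers the start time of the next meal and the number of non-missing measures satisfies the required minimum number", a standardized AUC is derived. No formula for the standardization is given.

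**The concern.** Appendices 2.2 and 2.8.1 cannot both be followed for iAUC. One keeps the session and shortens it; the other gives it no value. The SAP thus permits two analysis datasets for the CGM primary endpoint, and the choice falls to whoever programs the derivation.

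Following Appendix 2.2 would also produce a poorly defined number, for two reasons. The iAUC is a plain sum, so a shortened session would enter the visit average as if it were complete. And the end value G_k is averaged over 0 to 14 minutes after the last time point of the window. If the window ends at TN0, those readings belong to the next meal.

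**Working it through.** **1. The plan's own figure.** Appendix 2.2 expects 288 readings a day, that is 12 an hour, one every 5 minutes, or 24 in 2 hours. Its example for iAUC 0-2 h "requires at least 70% of the 24 measures (ie, at least 17 measures) during the 2 hour time window". Check: 0.70 × 24 = 16.8, rounded up to 17. The next-meal rule says more than 70% rather than at least 70%, but gives the same count, since 17/24 = 70.8%. The figure reproduces.

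**2. When the two rules diverge.** Seventeen readings at 5-minute spacing cover 17 × 5 = 85 minutes, or 16 × 5 = 80 minutes if the first falls at minute 0. So a next meal at about 80-85 to 120 minutes gives a truncated iAUC under Appendix 2.2 and none under Appendix 2.8.1. For the longer windows:

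- 3 h: 0.70 × 36 = 25.2, so 26 readings, about 26 × 5 = 130 minutes.
- 4 h: 0.70 × 48 = 33.6, so 34 readings, about 34 × 5 = 170 minutes.

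**3. What truncation can remove.** For 2 h, at most 24 − 17 = 7 readings, and 7/24 = 29.2%. This limits readings, not area.

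**4. Effect on one session.** The table applies the trapezoid sum of G − G_0 to assumed curves on a 1-minute grid, without the G_k averaging, and compares a cut at 85 minutes with the full 120 minutes. The curves are assumptions; the documents give none.

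| Assumed increment over pre-meal (mg/dL) | iAUC to 120 min | iAUC to 85 min | Change |
|---|---|---|---|
| Flat, +50 | 6000 | 4250 | −29.2% |
| Peak of 80 at 60 min, slow decline | 7750 | 5400 | −30.3% |
| Peak of 80 at 90 min | 7534 | 4772 | −36.7% |
| Linear rise to 80 at 120 min | 4800 | 2408 | −49.8% |
| Sine, back to baseline at 120 min | 6111 | 4916 | −19.6% |
| Early peak, below baseline after 85 min | 2757 | 4329 | +57.0% |

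As a hand check on the linear case: 80 × 120/2 = 4800 and 80 × 85²/(2 × 120) = 2408. A curve that rises only after 85 minutes would lose its whole iAUC. Because the sum is signed, cutting off a negative tail raises it.

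**5. Effect on the visit mean.** Sessions are averaged within a visit. If a share f of sessions each loses 29.2%, and complete and truncated sessions would otherwise have the same mean, the visit mean shifts by f × 29.2%: 0.02 × 29.2% = 0.6% and 0.20 × 29.2% = 5.8%. The range for f is assumed. With 3 meals on each of 10 valid days (30 sessions), one such session moves the mean by 29.2%/30, about 1%.

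**The case against.** The best reply is that the SAP already indicates which section governs. Appendix 2.4 sends the reader to Appendix 2.8 for the iAUC derivation. Appendix 2.9 pairs Appendix 2.2 with valid data and Appendix 2.8 with derivation method. Appendix 2.8 refers back to 2.2 only for valid sessions, and its subsections on excursions, AUC and iAUC each carry their own next-meal rule. The definition of G_k makes sense only for a complete window. On this reading no truncated iAUC is ever formed.

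This makes Appendix 2.8.1 the more natural governing rule, but it does not remove the conflict. The Appendix 2.2 sentence is a derivation rule, not just a validity check. It covers meal-related outcomes without exception and follows directly on an example that uses iAUC 0-2 h. No sentence exempts iAUC.

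The second reply is that little is at stake, and much of it stands. Only three main meals taken with prandial insulin are timed, and only the first of each type per day is used, so unrecorded snacks cannot trigger the rule. Two such meals within 2 hours are probably uncommon. The 3 h and 4 h windows are likely more exposed, but those iAUCs are neither addendum objectives nor in the secondary comparison list of Appendix 2.5.

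A reader might infer from the 70% threshold that truncation understates iAUC by up to 30%. The documents do not support that: the threshold bounds the readings lost, the loss of area can be larger or smaller, and the sign can reverse. Nor do they support a claim that the treatment contrast is biased in a known direction, since overlap frequency and curve shape by arm are not given.

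**Conclusion.** The two next-meal rules for iAUC are incompatible, and the CGM primary endpoint is among the variables affected. This is a faulty stated rule rather than a missing detail, because Appendix 2.2 applied literally gives an unscaled sum and an end value taken after the next meal.

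The firm size is a cap of 7 of 24 readings (29.2%) in an affected 2 h session. The error in that session's iAUC depends on the curve. The 0.6% to 5.8% shift in the visit mean rests on an assumed 2% to 20% of sessions affected and an assumed loss of 29.2% in each. If Appendix 2.8.1 is what gets programmed, there is no truncation error at all. The CGM analyses carry no multiplicity adjustment and do not feed the HbA1c primary or gated tests. The point is worth correcting because the correction is nearly free.

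**What to change.** Add a sentence to Appendix 2.2: the truncation rule does not apply to iAUC; Appendix 2.8.1 governs, and a session whose next recorded main meal does not start after T is excluded from iAUC 0-T. The exclusion is specific to each window, so a session dropped from iAUC 0-4 h can still count for iAUC 0-2 h.

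Exclusion is preferable to time-scaling a truncated sum. Multiplying by 120/85 still leaves the linear curve 29.2% low and makes the sine curve 13.6% high, and G_k at TN0 would still need a new definition. Dividing only the truncated sessions by time would average mg/dL with mg·min/dL.

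The cost is SAP wording and probably a few lost sessions. No new data are needed. One consequence to accept is that iAUC and AUC over the same window will then rest on slightly different sessions.

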Appendix 2.8.2. Average Glucose Excursions

Average glucose excursions 0 to T hour(s) for each valid CGM meal session, will be calculated by averaging the excursions within the time frame 0- T and prior to the start time of next meal. The pre-meal glucose will use the average value within the time window [-19, 0] minutes relative to the start of the meal. The excursion at time T is calculated by deducting the glucose at time T by pre-meal glucose.

The average value from all valid CGM meal sessions at the same visit will be used in the analysis.

Appendix 2.8.3. Area under The Curve

Area under the curve (AUC) will be calculated using the standard trapezoidal rule by summing the trapezoid areas between two consecutive glucose measures in the prespecified time period (eg, 24-hour, or 1 hour after the morning meal).

Similar to $iAUC_{0-T}$, corresponding AUC_{0-T} will be derived. When the analysis time window covers the start time of the next meal and the number of non-missing measures satisfies the required minimum number, standardized AUC_{0-T} will be derived.

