Appendix 2.8.6. Glucose in Target Ranges, Hypoglycemia - or Hyperglycemia

The percentage of time within a glucose range (target, hypo- or hyperglycemia ranges) will be calculated as the number of observations within the specified range divided by the number of

observations in the time interval (eg, 24-hour period) on all valid CGM days at the same visit. The duration (in minutes) within the glucose range will then be calculated as the percentage of time within the glucose range times the length of the period (24 hour, 18 hour, and 6 hour, for the periods of 24-hour, daytime or nighttime, respectively).

For example, if a patient had a total of 13 observations with glucose values ≤ 70 mg/dL (3.9 mmol/L) out of a total of 270 non-missing observations recorded during the 24-hour period across a valid CGM day (with missing observations $< 30\%$ of 288 measures per day), the percentage of time spent in hypoglycemia during the 24-hour period for this patient on this day will be calculated as $13/270 = 4.8\%$. For a visit, the average percentage across all valid CGM days during the visit will be calculated and used for the calculation of the duration (in minutes) with hypoglycemia (glucose value ≤ 70 mg/dL [3.9 mmol/L]) during the 24-hour period for this patient by multiplying the average percentage with 1440.

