Appendix 2.9. List of Derived CGM Variables

The following variables will be derived based on valid CGM data and derivation method defined in [Appendix 2.2](#) and [Appendix 2.8](#) respectively.

- Incremental $AUC_{0-1\text{hour}}$, $AUC_{0-2\text{hours}}$, $AUC_{0-3\text{hours}}$, $AUC_{0-4\text{hours}}$ after the start of morning meal, midday meal, evening meal and all three meals during each CGM section up to 10 days
- Average glucose excursion 0 to 1, 2, 3, 4 hours after the start of morning meal, midday meal, and evening meal and all three meals during each CGM section up to 10 days
- Maximum glucose excursion within 4 hours after the start of morning meal, midday meal, evening meal and all three meals
- Maximum glucose within 4 hours after the start of morning meal, midday meal, evening meal and all three meals
- Time to the maximum glucose within 4 hours after the start of morning meal, midday meal, evening meal and all three meals

- Area under the curve for a 24-hour, daytime and nighttime period
- Area under the curve during the 1, 2, 3, 4 hours after the start of morning meal, midday meal, evening meal and all three meals corresponding to above iAUC
- Between-day glucose variability during a 24-hour, daytime and nighttime period
 - standard deviation
 - coefficient of variation
 - mean of daily differences
- Within-day glucose variability during a 24-hour, daytime, nighttime period and 0-4 hour during morning meal, midday meal, evening meal and all three meals
 - standard deviation
 - coefficient of variation
 - Inter-quartile range
 - low blood glucose index
 - high blood glucose index
 - blood glucose risk index
 - mean amplitude of glycemic excursions (MAGE-, MAGE+ and MAGE+/- combined)
- Duration (in minutes) and percentage of time with glucose values within target range 70 to 180 mg/dL (3.9 and 10.0 mmol/L), both inclusive for a 24-hour, daytime and nighttime period
- Duration (in minutes) and percentage of time with glucose values within target range 70 to 180 mg/dL (3.9 and 10.0 mmol/L), both inclusive for 0-1, 0-2, 0-3, 0-4 hours during morning meal, midday meal, evening meal and all meals
- Duration (in minutes) and percentage of time with glucose values within target range 70 to 140 mg/dL (3.9 and 7.8 mmol/L), both inclusive for a 24-hour, daytime and nighttime period

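### The 24-hour, daytime and nighttime CGM AUCs are trapezoid sums with no adjustment for observed time, so missing readings at the edge of a period lower them

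*SAP*

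**What the plan says.** SAP Appendix 2.9 lists "Area under the curve for a 24-hour, daytime and nighttime period" among the variables to be derived. Appendix 2.8.3 gives the rule: AUC is obtained "by summing the trapezoid areas between two consecutive glucose measures in the prespecified time period (eg, 24-hour, or 1 hour after the morning meal". The only standardized AUC in that section is for meal windows: "When the analysis time window covers the start time of the next meal and the number of non-missing measures satisfies the required minimum number", a standardized version is derived.

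Three other provisions determine what happens when readings are missing.

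- **Valid day.** Appendix 2.2 requires "at least 70% of the total measures (288 measures per day) that are supposed to be obtained". It applies the same 70% cut-point to meal sessions, but not to the daytime or nighttime part of a day.
- **No imputation.** Appendix 2.8 states: "No missing CGM values will be imputed".
- **End-value requirement.** For the meal iAUC, Appendix 2.8.1 says: "The derivation requires that G_0 and G_k values are both available". No such condition is stated for the clock-period AUCs.

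Time in range is handled differently. Appendix 2.8.6 divides by the readings actually observed and then scales to the period length ("24 hour, 18 hour, and 6 hour, for the periods of 24-hour, daytime or nighttime, respectively").

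**The concern.** A trapezoid sum covers only the time between the first and last reading in the period. A gap in the interior is bridged by a straight line between its neighbours. A gap at either edge has no neighbour on one side, so that time drops out of the area. Two patients with identical glucose can then have different AUCs because one sensor stopped earlier.

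Edge gaps are foreseeable. The sensor is worn in sessions of up to 10 days, so each session has a first and a last part-day. The night starts at midnight and lasts six hours, so a moderate gap can remove much of it while the day still passes the 70% rule.

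What is at stake is the meaning of these variables. A lower AUC would be read as lower glucose exposure when it may reflect missing readings. Appendix 2.2 says CGM outcomes are derived per patient and visit and summarized by treatment group, with treatment comparisons for continuous measures.

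**Working it through.** **Inputs.** Readings are 5 minutes apart (288 per day; Appendix 2.8 uses "non-overlapping intervals ('buckets') of 5 minutes over 00:00:00 to 23:59:59"). The periods are 24, 18 and 6 hours, that is 288, 216 and 72 readings. The documents give no glucose profile and no gap frequency, so both are assumed below.

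**The SAP's own figures.** 0.70 × 24 = 16.8, rounded up to 17, matches the minimum stated for a 2-hour meal session. 13/270 = 4.8% matches the time-in-range example.

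**Readings that may be missing on a valid day.** 0.70 × 288 = 201.6, rounded up to 202. So 288 − 202 = 86 may be missing, which is 86 × 5 = 430 minutes, or 7 h 10 min. That exceeds the 72 readings of a whole night.

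**Flat profile.** With n consecutive readings at constant glucose g, AUC = (n − 1) × 5 × g. The ratio to the complete value is therefore the ratio of the numbers of intervals. At 180 mg/dL the complete 24-hour AUC is 287 × 5 × 180 = 258,300 mg/dL × min. With the last 86 readings missing it is 201 × 5 × 180 = 180,900. With the same 86 missing mid-day it is 258,300 again, because the gap is bridged.

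| Valid day with | Period | Intervals observed / complete | Ratio |
|---|---|---|---|
| 86 readings missing at one edge | 24-hour | 201/287 | 0.700 |
| Last 86 readings missing | Daytime | 129/215 | 0.600 |
| Readings ending at 18:00 (216 present) | Daytime | 143/215 | 0.665 |
| Gap 00:00-02:00 (264 present) | Nighttime | 47/71 | 0.662 |
| Gap 00:00-03:00 (252 present) | Nighttime | 35/71 | 0.493 |

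**Dependence on the profile.** For 160 + 40 sin(three cycles per day) mg/dL, which peaks at 02:00, the two night gaps give 0.629 and 0.434. With the phase reversed they give about 0.70 and 0.56. The direction is the same and the size moves.

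**Average effect.** I assumed that 25% or 50% of days have one contiguous gap of 12 to 86 readings (1 to about 7 hours) at a random position, and simulated 20,000 days with the first sinusoid. Two ways of placing the gap were tried.

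| Gap placement | Mean nighttime ratio (25% / 50%) | Nights more than 10% low | Fall in 24-hour mean |
|---|---|---|---|
| Start anywhere, cut off at midnight | 0.985 / 0.969 | 3.4% / 7.0% | 0.4% / 0.9% |
| Wholly within the day | 0.979 / 0.961 | 4.7% / 8.8% | about 0.1% or less |

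**After standardization.** Dividing by the spanned time restores the flat profile exactly. In the simulation, with the 70% rule applied to the night as well, the SD of the nighttime ratio falls from about 0.09-0.14 to 0.01. In a harder case (180 ± 40 mg/dL, one cycle per day, 86 edge readings missing), the standardized 24-hour mean is 181.5 (end gap) or 193.6 (start gap) mg/dL against 180.1. That is an error of about 1% to 7.5%, where the raw sum is 29% or 25% low.

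**The case against.** The strongest reply is that little depends on these variables. Clock-period AUC is not an objective or endpoint in Table APP.2.1, not the primary CGM outcome (Appendix 2.4), and not among the secondary variables assigned a model (Appendix 2.5). Its comparison by treatment rests on a general sentence in Appendix 2.2, in a subset addendum with no multiplicity adjustment. This stands and sets the low priority.

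The SAP also has partial safeguards. An otherwise complete day on which readings start after 07:10 or stop before about 16:50 fails the 70% rule, so many part-days are excluded. If days are averaged within a visit, a short night is diluted: one night at 0.493 among ten otherwise complete nights gives (9 + 0.493)/10 = 0.949. This limits the problem but does not remove it. A day ending after about 16:50 is still valid, and a single night gap never makes a day invalid. With three nights the same gap gives (2 + 0.493)/3 = 0.831.

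A reader might infer that the plan scores missing time as zero glucose. It does not. It assigns no value, and the lost area is only an arithmetic consequence. A reader might also infer bias between the open-label and blinded arms. Nothing in the documents indicates that sensor coverage differs by arm, and Appendix 2.2 describes the addendum sensor as blinded. With equal coverage both means shrink by about the same proportion, and so does their difference.

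Finally, dividing by the spanned time is one convention among several, and it assumes that unobserved time resembles observed time. That is true, but the error left is much smaller than that of the raw sum.

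**Conclusion.** The point holds as a minor defect in a stated rule. Followed literally, Appendix 2.8.3 gives too low a 24-hour, daytime or nighttime AUC whenever readings are missing at the edge of the period. On a valid day with a flat profile, the 24-hour value can be as low as 70% of the complete one and the daytime value 60%. A night missing midnight to 02:00 or 03:00 gives about 66% or 49% (63-70% and 43-56% for the sinusoids tried). These are single-day illustrations under assumed profiles, not expected effects.

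Under the assumed gap frequency the nighttime mean falls by about 1.5-4% and the 24-hour mean by under 1%. The main harm is therefore noise. Differential bias is possible but not shown.

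The stronger inference, that the trial's main CGM or glycemic results are at risk, is not supported. HbA1c does not use these data. The CGM primary iAUC has its own start and end-value rule. The secondary endpoints are iAUC under that same rule, averages over readings, or proportions of observed readings.

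**What to change.** In Appendix 2.8.3, define the 24-hour, daytime and nighttime AUC as the trapezoid sum divided by the time from the first to the last reading in the period, multiplied by the period length (24, 18 or 6 hours). Reporting time-averaged glucose would serve equally well. Also require at least 70% of readings within the period itself: 0.70 × 216 = 151.2, so 152 for daytime, and 0.70 × 72 = 50.4, so 51 for nighttime. The 24-hour period already has its minimum of 202. Both steps follow conventions the SAP uses for time in range and for meal sessions.

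The cost is a few lines of SAP text, a small programming change and some lost data. Under the gap assumption above, about 4-9% of nights would drop out of the nighttime AUC, and some daytime periods would drop out too. The SAP should say whether the period-level minimum applies only to AUC or also to the other daytime and nighttime variables in Appendix 2.9.
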